**Table 2: Schedule of Visits and Procedures Dose Expansion (Phase 2)**

Assessment Period	Screening	Cycle 1 and Cycle 2									Cycle 3 and Beyond			Post-Treatment		
		Day -28 to 1	Day 1	Day 2	Day 3	Day 4	Day 5	Day 8	Day 11	Day 15	Day 22 b	Day 1	Day 8	Day 22 b	End of Treatment (+10 days)	Follow-up 3 mo
Informed consent c	X															
Inclusion/exclusion criteria	X	X														
Demographics	X															
Medical/cancer history d	X															
Medication history e	X															
Physical examination f	X	X					X		X g	X	X	X	X	X		
Vital signs h	X	X	X	X	X	X	X	X	X g	X	X	X	X	X	X	
ECOG performance status	X											X				
ECG i	X	X	X	X	X	X	X	X	X g	X	X	X	X	X		
ECHO j	X													X		
Pregnancy test k	X	X									X			X		
Hematology l	X	X	X	X	X	X	X		X g	X	X	X	X	X	X	
Serum chemistry m	X	X			X		X		X g	X	X	X	X	X	X	
Coagulation n	X	X			X		X		X g	X	X	X	X	X	X	
Additional labs o	X								X g		X o			X		

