## Footnotes:

- a. The acceptable visit window is + 1 day for Day 11 and  $\pm 1$  day for Day 8 and Day 15 and  $\pm 7$  days for the follow-up visit post-treatment. Visits may be skipped or postponed if prospectively identified by the Investigator (e.g., national holidays, subject holidays). If Day 4 visit is missed then Day 4 assessments must be done at the next in clinic visit. All procedures and examinations should be performed before the administration of study drug(s), except as indicated below.
- b. Assessments only applicable if dosing cycle is changed to 28-day cycle.
- c. The Institutional Review Board (IRB)-approved informed consent form (ICF) must be signed before any study-specific procedures or examinations are performed.
- d. An event occurring after the subject has provided informed consent, but before the first dose of study treatment, will be collected as medical history unless the event is either new and attributed to protocol-mandated procedures by the Investigator OR there is a significant change in the rate of occurrence or an increase in the severity of the pre-existing condition which is judged to be clinically important and attributed to the protocol-mandated procedures by the Investigator. Any new or clinically significant changes in the subject's medical and/or cancer history that occur immediately after the first dose of drug will be recorded as AEs.
- e. Include prior cancer treatments: previous immunotherapy, chemotherapy, targeted therapy, radiation, OTC medications, herbs and dietary supplements
- f. Physical examinations at screening/baseline, at day 1 of each cycle, and at end of treatment should be complete assessments (evaluate all major organ systems, including the following categories: general, head, eyes, ears, mouth/throat, neck, heart, lungs, abdomen, lymph nodes, joints, extremities, integumentary, neurologic, and psychiatric). Other examinations may be focused, at the discretion of the Investigator, to identify changes from baseline or evaluate changes based on the subject's clinical symptoms. Weight is to be reported at each visit, height at screening/baseline visit only.
- g. Assessments not applicable if dosing cycle is changed to 14-day cycle.

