- l. Hematology performed at the indicated times by a central laboratory: red blood cell (RBC) count, hemoglobin (Hgb), hematocrit (Hct), mean corpuscular volume (MCV), platelet count, white blood cell (WBC) count, and WBC differential (neutrophils, lymphocytes, monocytes, eosinophils, and basophils), mean corpuscular hemoglobin (MCH), mean corpuscular hemoglobin concentration (MCHC) ([Appendix 1](#)). If hematology demonstrates CTCAE grade 3/4 cytopenias, increase frequency to daily monitoring as clinically appropriate. Hematology assessments scheduled for the day of study drug dosing must be available and assessed for toxicity before dosing. The sampling for hematology assessment can be drawn up to 24 hours prior to dosing.
- m. Serum chemistry performed at the indicated times by a central laboratory: sodium, potassium, calcium, chloride, creatinine, calculated creatinine clearance (Cockcroft-Gault), total bilirubin, albumin, alkaline phosphatase, CO2 or bicarbonate, lactate dehydrogenase (LDH), aspartate aminotransferase (AST), alanine aminotransferase (ALT), glucose, blood urea nitrogen (BUN), total protein (TP), gamma-glutamyl transferase (GGT), and uric acid ([Appendix 1](#)).
- n. Coagulation performed at the indicated times by a central laboratory: partial thromboplastin time and prothrombin time ([Appendix 1](#)).
- o. Additional tests performed at screening, on Day 15 of Cycle 1 and 2, and at End of Treatment: thyroid stimulating hormone, lipase, amylase, free thyroxine (T4), creatine kinase, HLA typing (only at screening) and on Day 1 beginning from Cycle 4 ([Appendix 1](#)).
- p. Microscopy is required only to follow-up clinically significant urine dipstick findings. List pH, specific gravity, protein, glucose, ketones, bilirubin, blood, and leukocyte esterase ([Appendix 1](#)).
- q. Serology tests include hepatitis B surface antigen (HBsAg), hepatitis C virus antibody (anti-HCV), and human immunodeficiency virus (HIV) antibody ([Appendix 1](#)).
- r. Unstained formalin-fixed, paraffin embedded, archival tumor tissue sections on slides are acceptable.

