### **6.3 Treatment Period**

Subjects who meet the selection criteria may start NKTR-214 treatment within 28 days following the Screening visit. The treatment period of the study is divided into multiple 21-day cycles with associated evaluations and procedures. Results of the assessments must be reviewed and documented before administering the first dose of the next cycle. No subject will be permitted escalation of dose level after assignment to a specific NKTR-214 dose level. Dose reductions after Cycle 1 due to AEs may occur following a discussion with the site Investigator and Medical Monitor. Every effort should be made to schedule visits within the protocol-specified windows.

For each dose level in Part 1, the first subject enrolled into a given dose cohort will be treated and monitored from Cycle 1, Day 1 through Cycle 1, Day 5 for safety and tolerability prior to dosing of additional subjects at that dose level.

Cycle 1, Day 1 will be the first day of treatment with NKTR-214 and Cycle 2, Day 1 will be the first day of the second dose of NKTR-214. Results from Day 1 laboratory evaluations must meet eligibility criteria prior to Cycle 1, Day 1 dosing.

During dose escalation, subjects who drop out prior to completion of Cycle 1 will be replaced unless the subject discontinued due to a DLT. During dose expansion, subjects will not be replaced.

Subjects will be treated until unacceptable toxicity, or disease progression per RECIST version 1.1. In the presence of disease progression, treatment may continue if there is clinical benefit as determined by the Investigator based on a reduction of symptoms related to cancer and absence of clinical deterioration or decline in ECOG performance status.

Note: Dosing may change to q14d or q28d following review and agreement by the Sponsor and Investigators. The change in cycle length will be determined by review of safety data and PK review of study drug.

After completing the pre-dosing procedures, administer NKTR-214 as an IV infusion over  $15 \pm 5$  minutes (Section 6.11).

Postdosing:

- The study site must be equipped for medical emergencies and have access to an intensive care unit.
- During dosing days, subject will stay in clinic for observation approximately 1 hour after dosing.
- Administer at least 2 liters of fluid (IV or self-administered orally [e.g., fluid containing electrolytes]) during Days 1 to 5 of every cycle.

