### **6.5 Post-treatment Period**

The EOT/Early Termination visit is to occur within 30 days (+ 10 days) after last dose of study drug.

Subjects who reach the EOT visit without radiographic disease progression must continue to undergo immunogenicity testing and radiological assessment at the interval of every 3 months ( $\pm 7$  days) until either disease progression per RECIST version 1.1 or the start of a new anti-cancer therapy. Subjects will also be followed every 3 months ( $\pm 7$  days) for survival until death, lost to follow-up, study termination by Sponsor, or 3 years have passed since the subject's first dose.

For any toxicity the Investigator attributed to study drug, the Investigator will assess the subject to determine whether the toxicity resolved or worsened. Information on whether the toxicity resolved or worsened must be entered into the eCRF.

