## **8.0 ASSESSMENT OF SAFETY OR AES AND SERIOUS AES**

### **8.1 AE Definition and Assessment**

An AE is defined as any untoward medical occurrence in a clinical investigation subject administered a pharmaceutical product, at any dose, not necessarily related to the treatment.

An AE can therefore be any unfavorable and unintended sign, symptom, or disease temporally associated with the use of a medicinal product, whether or not considered related to the medicinal product. An AE can also arise from any use of the drug and from any route of administration, formulation, dose, or overdose. This definition includes intercurrent illnesses or injuries, and exacerbation of preexisting conditions. Clinical laboratory abnormalities will only be reported as AEs if they are deemed clinically significant by the Investigator and/or are associated with signs and symptoms, require treatment, or require follow-up.

An AE does not include:

- A medical or surgical procedure (e.g., surgery, endoscopy, tooth extraction, or transfusion); an AE is the underlying condition that leads to the procedure
- Pre-existing diseases or conditions present or detected before start of study medication administration which do not worsen or increase in severity or frequency after the administration of study medication
- Situations where an untoward medical occurrence has not occurred (e.g., hospitalization for elective surgery for a condition that has not worsened on study, social and/or convenience admissions to grant families a respite in caring for a subject)
- Overdose of either study medication or concomitant medication without any signs or symptoms

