#### 10.2.1 Expansion Cohorts Safety Monitoring

Bayesian sequential monitoring will be employed to perform ongoing safety monitoring targeting a toxicity rate of not more than 30% (where toxicity follows the same definition as a DLT defined in Section [4.1.2.1](#)) for the first 80 subjects enrolled in the dose expansion phase. Subjects will be monitored across tumor-specific cohorts after a minimum of 6 subjects treated at the selected dose for the dose expansion phase. The criteria for suspending enrollment due to safety are included in [Table 7](#) based on Bayesian sequential monitoring designs by [Thall et al. \(1995\)](#). The determination of the criteria is when:

$$\Pr [\text{prob}(\text{toxicity}) > 0.30 \mid \text{data}] > 0.95.$$

If there is a greater than 95% chance that the toxicity rate is greater than 30%, then accrual will be suspended and the safety review committee will meet to review safety data including aggregated safety summaries. We assume a beta (0.6, 1.4) prior distribution for the toxicity rate,

which has a mean of 0.3 corresponding to the 30% target toxicity rate. A constant 30% rate was chosen for the standard treatment rate.

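### On a 14-day cycle, Table 2 drops the Day 15 thyroid, pancreatic-enzyme and creatine kinase tests without moving them, so the first scheduled on-treatment test is Day 43, after three doses

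*Protocol*

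**What the plan says.** In Table 2 of the Protocol, the row named "Additional labs" is marked at Screening, at Day 15 of Cycles 1 and 2 (superscript g), at Day 1 of Cycle 3 and beyond (superscript o), and at End of Treatment. The Day 1 cell for Cycles 1 and 2 is blank.

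- Footnote o gives the timing: "Additional tests performed at screening, on Day 15 of Cycle 1 and 2, and at End of Treatment: thyroid stimulating hormone, lipase, amylase". It goes on to free T4 and creatine kinase and ends "HLA typing (only at screening) and on Day 1 beginning from Cycle 4", so testing on Day 1 starts at Cycle 4, not Cycle 3.
- Footnote g reads "Assessments not applicable if dosing cycle is changed to 14-day cycle". It names no replacement day.
- Protocol Section 6.3 says "Results of the assessments must be reviewed and documented before administering the first dose of the next cycle".
- Protocol Section 6.5 says the End of Treatment "visit is to occur within 30 days (+ 10 days) after last dose of study drug".

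The 14-day cycle is an expressly permitted option. The synopsis lists it for Part 2, Sections 4.1.2.1 and 6.3 allow the change, and SAP Section 8.8 provides for it when computing exposure.

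**The concern.** The omission looks like an oversight. The other visible Table 2 rows with a g-marked Day 15 cell are physical examination, vital signs, ECG, hematology, chemistry and coagulation. Each also has a mark on Day 1 of Cycles 1 and 2. On a 14-day cycle, Cycle 2 Day 1 is study Day 15, so those assessments still take place. The additional-labs row has no such mark, and its test is lost.

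Two things are at stake.

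- **Subject safety.** Thyroid, pancreatic-enzyme or creatine kinase toxicity may be found only after doses 2 and 3 have been given. The plan treats most of these analytes as important: SAP Appendix 16.2 lists TSH, amylase and lipase abnormalities among the special-interest terms.
- **Toxicity counts.** DLTs are Cycle 1 events, and for the Table 7 suspension boundaries Section 10.2.1 says "toxicity follows the same definition as a DLT". On a 14-day cycle, no scheduled test within Cycle 1 can detect a symptomless but clinically significant Grade 3 or higher rise in these analytes.

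**Working it through.** **Inputs.** Panel timing is from Table 2 and its footnotes g and o. Day 1 of each cycle is the dosing day (Section 6.3). Procedures precede dosing unless stated otherwise (Table 2 footnote a). Dosing is assumed to follow the given cycle length from Cycle 1, without delay.

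**Formula.** With cycle length L, Day 1 of cycle k is study day 1 + L(k − 1), and Day 15 of cycle k is study day 15 + L(k − 1).

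**Default 21-day schedule first.**
- Cycle 1 Day 15 = 15.
- Cycle 2 Day 15 = 15 + 21 = 36.
- Cycle 4 Day 1 = 1 + 21 × 3 = 64.
- Cycle 5 Day 1 = 1 + 21 × 4 = 85.

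**28-day schedule.**
- Cycle 1 Day 15 = 15.
- Cycle 2 Day 15 = 15 + 28 = 43.
- Cycle 4 Day 1 = 1 + 28 × 3 = 85.

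**14-day schedule.** Both Day 15 tests are cancelled.
- Cycle 4 Day 1 = 1 + 14 × 3 = 43.
- Day 1 of Cycles 5, 6 and 7 = 57, 71 and 85.

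| Cycle length | Dose days | Panel days through Day 85 | Doses before first panel | Panels through Day 42 | Panels through Day 85 |
|---|---|---|---|---|---|
| 14 days | 1, 15, 29, 43, 57, 71, 85 | 43, 57, 71, 85 | 3 | 0 | 4 |
| 21 days | 1, 22, 43, 64, 85 | 15, 36, 64, 85 | 1 | 2 | 4 |
| 28 days | 1, 29, 57, 85 | 15, 43, 85 | 1 | 1 | 3 |

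The delay on the 14-day cycle is 43 − 15 = 28 days, and 3 − 1 = 2 more doses are given before the first test.

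**New on-treatment result scheduled before doses 2 and 3.**
- 21 days: 2 of 2 (Day 15 before the Day 22 dose, Day 36 before the Day 43 dose).
- 28 days: 2 of 2 (Day 15 before the Day 29 dose, Day 43 before the Day 57 dose).
- 14 days: 0 of 2.

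**Early stoppers on the 14-day cycle.** They are next tested at End of Treatment. After a single dose on Day 1 that visit is due by Day 31, or Day 41 with the extra 10 days. After a second dose on Day 15 it is due by Day 45 (55), and after a third on Day 29 by Day 59 (69). The test may therefore fall before or after Day 43, but it comes once treatment has ended.

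**With the two tests moved to Day 1 of Cycles 2 and 3.** Panels on the 14-day cycle fall on Days 15, 29, 43, 57, 71 and 85. The first three follow 1, 2 and 3 doses, the same pattern as on the other two schedules.

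**The case against.** The reading of the table and the Day 43 arithmetic are not in dispute. The case on the other side concerns consequence.

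- **The 14-day cycle is optional.** The base schedule is every 21 days, and nothing shows that 14 days was chosen for Part 2. That is true, and the point matters only if that option is used. A schedule written for an option should still work when the option is taken.
- **The DLT effect is thin.** Section 8.1 says "Clinical laboratory abnormalities will only be reported as AEs if they are deemed clinically significant by the Investigator" or if they come with symptoms, treatment or follow-up, and the DLT definition excludes laboratory changes that are not clinically significant. Symptomatic events can surface at the retained visits, and Section 8.11 lets investigators order further tests. This stands. What remains is a symptomless rise judged significant because it needs treatment or follow-up. Bias in the Table 7 count is possible but not shown.
- **Section 6.3 does not require this panel in every cycle.** No panel is scheduled in Cycle 3 on the 21- and 28-day cycles, and only hematology must be available before dosing. This also stands. The comparison of 0 of 2 with 2 of 2 describes the information available at the review; it does not show a breach of a protocol rule.
- **A draw on the dosing day may come too late for that dose.** Part 2 uses a central laboratory. The moved Day 15 draw may not inform dose 2, although it should inform dose 3 on Day 29. That is still better than no result.
- **Part 1 is not verified.** Table 1 footnotes g and p have matching wording, but its additional-labs row could not be checked. The same gap there, and any effect on the 3+3 decisions, is probable only.

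**Conclusion.** The concern holds for Table 2. On a 14-day cycle followed from the start without delay, the first scheduled on-treatment TSH, free T4, lipase, amylase and creatine kinase results come on Day 43 after three doses, against Day 15 after one dose on the other two schedules. Dose delays would push Day 43 later.

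The consequence is limited. The number of draws catches up by Day 85, the other main safety assessments stay in place, and special-interest event rates over full follow-up are not shown to be lower. The size of any DLT undercount cannot be derived from the documents. The change is recommended because early monitoring is weakest on the most dose-dense schedule and the remedy is cheap.

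**What to change.** Add one sentence to Table 2 footnote o, and to Table 1 footnote p if its Day 15 cell also carries g:

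*On a 14-day cycle, the Day 15 tests of Cycles 1 and 2 are drawn pre-dose on Day 1 of Cycles 2 and 3, and reviewed before dosing where results are available.*

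To allow for central-laboratory turnaround, the window that footnote l gives for hematology (sampling up to 24 hours before dosing) could be extended to these tests.

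A second sentence is optional. The Cycle 2 Day 1 pre-dose sample reflects Cycle 1 exposure only, so an abnormality in it that meets DLT criteria could be attributed to Cycle 1. That changes DLT accounting and should be decided separately. The draw should be moved either way.

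The cost is up to two small tubes per subject on the 14-day cycle, at visits where hematology and chemistry are already drawn. Through Day 85 that schedule would have 6 panels, against 4 on the 21-day and 3 on the 28-day cycle.

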## 2.0 INTRODUCTION

### 2.1 Background

Activating the immune system has the potential to produce durable responses in human cancers (Hodi, 2010). Recent attention in immunotherapy has focused on immune activation using checkpoint inhibitor antibodies (Topalian, 2014; Robert, 2014). However, direct immune stimulation using cytokines can also drive immune-mediated cancer cures (Hanzly, 2014). Aldesleukin directly stimulates the immune system and has been shown to lead to durable responses in ~10% of people with metastatic melanoma and renal cancer (Payne, 2014). However, in addition to aldesleukin acting as a stimulator of the immune system by activating tumor killing CD8+ T cells (CD8T), it also suppresses the immune system by activating regulatory T (Treg) cells (Boyman, 2012). Despite favorable clinical outcomes associated with aldesleukin, it has several therapeutic limitations including the need for inpatient hospital administration, 5 consecutive days of dosing, and the potential for serious toxicities, comprising capillary leak syndrome, hypotension and pulmonary edema requiring medical management in the intensive care unit.

A novel cytokine with optimized immune system activation and the targeted profile of NKTR-214 (i.e., a superior safety profile allowing for outpatient administration and a longer duration of action requiring less frequent dosing) would potentially be an important advancement for the treatment of patients with cancer. NKTR-214 consists of IL-2, which has the same amino acid sequence as aldesleukin, conjugated at a defined region within the protein to releasable polyethylene glycol (PEG) chains. The PEG chains render the molecule inactive. After administration *in vivo*, the PEG chains are slowly hydrolyzed to generate active cytokine conjugates. The most active IL-2 conjugates are the 2-PEG-IL2 and 1-PEG-IL2. Presumably, the location of the PEG chains on the active conjugated-IL-2 reduces the affinity to the IL2 receptor alpha subunit (IL2R $\alpha$ ), responsible for activating the undesirable Treg cells to a greater extent than the affinity to the IL-2-receptor beta subunit (IL2R $\beta$ ) relative to aldesleukin. In the tumor, NKTR-214 preferentially activates CD8+ T cells over Tregs. In addition, NKTR-214 provides sustained exposure to active 1-PEG and 2-PEG-IL2 in tumor.

### 2.2 Pre-clinical Data

#### 2.2.1 Pharmacology

Pharmacology studies investigated the mechanism of action, as well as *in vitro* and *in vivo* activity of NKTR-214 using cell lines and syngeneic tumor models. After administration *in vivo*, PEG is slowly hydrolyzed from NKTR-214 to generate active conjugated IL-2 forms, 2-PEG-IL-2 and 1-PEG-IL-2. Presumably, the location of the PEG chains on IL-2 interferes with the interaction to the receptor that activates the undesirable Treg cells in the tumor

(Charych, 2013a). As such, this receptor bias markedly increases the ratio of tumor killing CD8 T cells to Treg cells in tumors (to > 400) (Charych, 2013b). At the same time, the active conjugated IL-2 species released from NKTR-214 have different pharmacokinetic properties compared to aldesleukin, leading to a sustained and higher exposure in the tumor compared to an equivalent dose of aldesleukin (Hoch, 2013). NKTR-214, as a single agent, showed marked tumor growth suppression in the B16F10 mouse melanoma model, requiring a 10-fold lower cytokine equivalent dose that is administered once every 9 days, compared to twice daily dosing required for aldesleukin. The combinatorial immunity mediated by NKTR-214 induced CD8+ T cell activation and checkpoint blockade (anti-CTLA-4 and anti-PD-1) was synergistic, producing durable responses in multiple murine models of human cancer. Rechallenge and immune cell depletion studies assessing the anti-tumor activity induced by NKTR-214 combined with anti-CTLA-4 in the EMT6 murine breast tumor model demonstrated synergistic efficacy that was specific, durable, and dependent on both CD8T and NK cells. In all nonclinical species tested, NKTR-214 resulted in stimulation of several markers of immune system activation, in particular lymphocyte counts and sCD25.

### 2.2.2 Pharmacokinetics

Pharmacokinetic data in mice, rats, and monkeys demonstrated that a single dose of NKTR-214 provides sustained exposure to active conjugated IL-2 metabolites in both plasma and tumor. Exposure to NKTR-214 and active metabolites was consistent across nonclinical animal species. Active 2-PEG-IL-2 and 1-PEG-IL-2 are released gradually over 24 to 48 hours and decline in parallel to NKTR-214, at half-lives between 15-20 hours. No differences were observed between male and female animals, and accumulation was less than 2-fold after repeat administrations every 14 days. The NKTR-214 PK/ADME profile of gradual formation of and sustained tumor exposure to active 2-PEG-IL-2 and 1-PEG-IL-2 appears responsible for improved safety profile and antitumor activity in animals.

